Study Title: Respiratory Mechanics Following Brain Injury: The role of inhaled nitric oxide

Principal Investigator: [name]

Sponsor: USAF 711th Human Performance Wing

- 1. Length of time for research**
 - a. 18 months patient enrollment and data collection
 - b. 6 months data analysis and preparation of manuscript
- 2. Research Location(s):** All subjects will be patients in the surgical or neurosurgical intensive care unit at the University of Cincinnati Medical Center. Study records will be maintained in the researchers' office in the MSB.
- 3. Abstract/Brief Overview:**

Intubation and mechanical ventilation are common treatments in the care of patients with traumatic brain injury (TBI). Intubation allows for airway control and facilitates removal of respiratory secretions. Mechanical ventilation allows control of arterial carbon dioxide to aid in control of intracranial pressure. Recent evidence suggests that lung protective ventilation (tidal volumes of 6 ml/kg of predicted body weight and moderate positive end expiratory pressure) improves outcomes following brain injury and reduces brain-lung cross talk.

The treatment of respiratory failure in TBI must balance the need to improve lung function with the negative consequences of increased intrathoracic pressure on mean arterial pressure, intracranial pressure and venous return. Traditional treatment of increasing positive end expiratory (PEEP) and mean airway pressure then, represent competing interests. Methods for improving arterial oxygenation while avoiding negative hemodynamic effects are needed.

The impact of head injury on respiratory mechanics has been studied in just a few clinical investigations. (1-3) Of note, the earliest of these noted that the ventilation perfusion (V/Q) matching following TBI was not the result of lung collapse or parenchymal lung disease but secondary to alterations in perfusion. There are three possibilities for this finding:

1. redistribution in regional perfusion, which is partially mediated by the hypothalamus
2. pulmonary microembolism, leading to increased dead space
3. lung surfactant depletion due to excessive sympathetic stimulation and hyperventilation.

The introduction of inhaled pulmonary vasodilators such as inhaled nitric oxide or aerosolized epoprostenol offer an opportunity to improve oxygenation in patients with TBI without increasing airway pressures in the face of V/Q inequalities.

This study will evaluate the changes in respiratory mechanics following TBI and determine the effect of inhaled nitric oxide on gas exchange.

4. Purpose of Study:

[figure not shown]
To determine the changes in respiratory mechanics in patients with traumatic brain injury (within 36 hours of admission and day 3 following admission).

To evaluate the effect of inhaled nitric oxide on gas exchange in patients with traumatic brain injury within 36 hours of admission.

Hypothesis: Inhaled nitric oxide improves oxygenation and reduces deadspace to tidal volume ratio following TBI.

5. Background:

Intubation and mechanical ventilation are common treatments in the care of patients with traumatic brain injury (TBI). Intubation allows for airway control and facilitates removal of respiratory secretions. Mechanical ventilation allows control of arterial carbon dioxide to aid in control of intracranial pressure. Recent evidence suggests that lung protective ventilation (tidal volumes of 6 ml/kg of predicted body weight and moderate positive end expiratory pressure) improves outcomes following brain injury and reduces brain-lung cross talk. Figure 1.

Respiratory failure following traumatic brain injury is a common complication resulting in hypoxemia and is associated with release of inflammatory mediators which may damage distal organs including the brain. The etiology of respiratory

failure following brain injury is multifactorial. Isolated head trauma is associated with neurogenic pulmonary edema and changes in ventilation perfusion matching. Concomitant trauma to the chest and pulmonary contusion may further worsen lung injury. It has been suggested that brain injury primes the lung to be a greater risk to a second hit (pneumonia, ventilator induced lung injury, lung contusion). Loss of consciousness can lead to aspiration of oral or gastric contents leading to pneumonia. Importantly, respiratory failure following TBI is implicated in 50% of deaths and prolonged ICU and hospital stay. (4,5)

The treatment of respiratory failure in TBI must balance the need to improve lung function with the negative consequences of increased intrathoracic pressure on mean arterial pressure, intracranial pressure and venous return. Traditional treatment of increasing PEEP and mean airway pressure then, represent competing interests. Methods for improving arterial oxygenation while avoiding negative hemodynamic effects are needed.

The impact of head injury on respiratory mechanics has been studied in just a few clinical investigations. (1-3) Of note, the earliest of these noted that the ventilation perfusion (V/Q) matching following TBI was not the result of lung collapse or parenchymal lung disease but secondary to alterations in perfusion. There are three possibilities for this finding:

1. redistribution in regional perfusion, which is partially mediated by the hypothalamus
2. pulmonary microembolism, leading to increased dead space
3. lung surfactant depletion due to excessive sympathetic stimulation and hyperventilation.

The introduction of inhaled pulmonary vasodilators such as inhaled nitric oxide or aerosolized epoprostenol offer an opportunity to improve oxygenation in patients with TBI without increasing airway pressures in the face of V/Q inequalities.

In 1983, Cooper and Boswell demonstrated that hypoxemia in a series of 21 patients with head injury was related to a decrease in functional residual capacity and increased shunt. (2) In this study the addition of 10 cm H₂O PEEP reversed the fall in FRC and improved oxygenation. However, these patients were all paralyzed and nursed in the supine position. Paralysis and the supine position are known to decrease FRC even in normal subjects under anesthesia.

More recently, Koutsoukou et al evaluated 21 subjects with brain injury (intracranial hemorrhage and TBI) and no evidence of acute lung injury and found that PEEP of 10 cm H₂O prevented a deterioration in respiratory mechanics at five days. On day 1, PaO₂/FIO₂ was > 400 (FIO₂= 0.46) but both lung elastance and airways resistance were slightly elevated in both groups. These findings are not

unexpected in the presence of an endotracheal tube in a sedated subject lying in bed head up. These changes in respiratory mechanics worsened after day 5 and only elastance was spared in the group receiving 10 of PEEP. (3)

Mechanical ventilation following TBI is provided with the normal goals, reduce the work of breathing, provide adequate oxygenation, maintain normo- or hypocapnia and avoid lung injury. However, in an effort to improve brain tissue PaO_2 (TbO_2) mechanical ventilation in TBI may include increases in mean airway pressure and FIO_2 unrelated to the degree of lung dysfunction. Ventilatory support is always a balance of competing interests. Increases in airway pressure by increasing tidal volume, prolonging inspiratory time or increasing PEEP must be balanced against the risk of lung injury and hemodynamic interference. In TBI these must be furthered balanced against the impact on mean arterial pressure, cerebral perfusion pressure and venous return. (6)

Inhaled nitric oxide (INO) is a selective pulmonary vasodilator that at low doses (5-20 ppm) improves V/Q matching and at higher doses (80 ppm) reduces pulmonary artery pressures. Nitric oxide plays a role in a number of biologic processes and pathways that have been associated with improvements in brain function. (7,8) INO has been used in patients with TBI with successful increases in oxygenation in small case series. (10-11). These reports are not systematic applications of INO but rather rescue therapy in the face of ARDS.

The use of INO in ARDS has not proven to impact outcomes. (12-13) Several studies have shown improved gas exchange but no changes in morbidity or mortality. Despite these findings, INO is often used in ARDS to help improve gas exchange without increasing the risk of lung injury by increasing lung volumes or pressures.

This study will determine the etiology of lung dysfunction following TBI and describe the effect of INO on cardiorespiratory variables.

Inhaled nitric oxide (INOmax) is FDA approved and delivered via the INOmax DS_{IR} and FDA cleared delivery and monitoring device. The use of inhaled nitric oxide is limited to a maximum of 80 ppm. We will deliver 20 ppm, a dose that is widely prescribed.

6. Study design:

This study will determine the impact of inhaled nitric oxide on gas exchange and hemodynamics in a series of up to 43 patients with TBI over an 18 month period. The delivery of INO will be blinded. The study will also describe the changes in respiratory mechanics over a 3 day period.

All subjects \geq 18 years of age, admitted to the University of Cincinnati Medical Center with traumatic head injury requiring mechanical ventilation within 24 hours of admission will be screened for enrollment.

Following informed consent, patients will have assessments of respiratory function accomplished using the existing monitors within the mechanical ventilator. The NM3 respiratory monitor and airway sensor will be placed for continuous recording of data. Within 36 hours of admission, the following measurements will be made by the study staff:

1. Static and dynamic lung compliance using tidal volume and airway pressures ($CL_{static} = P_{plat} - P_{PEEP}/VT$) $CL_{dynamic} = P_{plat} - P_{PEEP}/VT$). These measurements are made non-invasively using the integral monitoring of the mechanical ventilator.
2. Airway resistance using airway pressures and flow ($Raw = P_{plat} - P_{PEEP}/Mid Expiratory flow$). These measurements are made non-invasively using the integral monitoring of the mechanical ventilator.
3. Dead space to tidal volume ratio (V_d/V_t) will be calculated using the Enghoff modification of the Bohr equation: $V_d/V_t = PaCO_2 - PeCO_2/PaCO_2$, where V_d is the dead space volume and V_t is the tidal volume; $PaCO_2$ is the partial pressure of carbon dioxide in the arterial blood, and $PeCO_2$ is the mixed expired partial pressure of carbon dioxide in the expired (exhaled) air. In the absence of arterial blood gases we will calculate $PaCO_2$ from determination of alveolar concentrations ($PaCO_2$) in expired gas.
4. Functional residual capacity (FRC) will be measured by the automated system within the GE Carestation ventilator, which uses a step change in FIO_2 to measure FRC through nitrogen washout while monitoring oxygen consumption and carbon dioxide production. These measurements are made non-invasively using the integral monitoring of the mechanical ventilator.
5. Positive end expiratory pressure (PEEP) will be titrated from baseline PEEP as set at time of enrollment to 15 cm H_2O (in 5-cm H_2O increments) while measuring all the variables listed in #1-4 above. This method will determine the best PEEP and determine recruitability of the lung. FRC will be measured at three levels of PEEP from baseline to a maximum of 15 cm H_2O . This is an automated measurement requiring approximately 15 minutes to complete. If the patient develops hypotension (systolic pressure < 90 mm Hg or mean arterial pressure < 60 mm Hg) participation in the PEEP trial will be terminated.
6. Following these initial measurements, patients will be randomized to receive either a placebo (nitrogen and oxygen) or inhaled NO at 20 ppm for 2 hours \pm 30 minutes. After receiving the placebo or inhaled NO, the measurements in #1-4 will be reassessed (no change in PEEP will be made during this time unless required for clinical purposes).
7. If the patient remains on the ventilator at day 3 (72 hours after admission), 1-6 above will be repeated.

Subjects will receive placebo or drug for no more than 5 hours total.

If the patient responds to NO with a brisk increase in SpO₂ or PaO₂ – sudden withdrawal of NO can result in a fall in oxygenation (rebound pulmonary hypertension). This is uncommon in the absence of pulmonary hypertension. Prevention of rebound pulmonary hypertension is accomplished by increasing FIO₂ by 10-20% prior to discontinuation of NO, followed by a return to baseline FIO₂ over 30 mins.

If ICP goes up by >20% NO will be discontinued.

7. Research data collection/study procedures:

The patient baseline demographics including injury mechanism, severity and distribution, Glasgow coma scale score, age, gender, any witnessed aspiration, and lung mechanics measurements listed above will be collected to data sheets and then entered into a RedCap database. We will also record ventilator settings, lung compliance, airways resistance, dead space to tidal volume ratio, functional residual capacity, blood gases and duration of total mechanical ventilation, days in the ICU, hospital days and survival will be collected from the medical record and also entered into the RedCap database. See sequence of events for study measures.

8. Specimen collection:

The following blood samples will be taken:

At baseline up to 3.5 ml will be taken. 1.5 ml for arterial blood gas testing (tests include: arterial pH, PaCO₂, PaO₂, SaO₂ and HCO₃) and 2 ml for measurement of inflammatory mediators specific to the lung.

After 90 to 120 minutes of nitric oxide/placebo delivery, less than 1.5 ml will be taken for arterial blood gas testing.

At the end of the study, up to 3.5 ml will be taken. 1.5 ml for arterial blood gas and 2 ml for measurement of inflammatory mediators specific to the lung.

The blood will be taken from indwelling lines when possible. If we are unable to obtain any of the blood samples, the subject will remain in the study and all other data will continue to be collected

9. Potential Benefits:

The detailed measurement of respiratory mechanics will be provided to the clinical team. This information which is not routinely measured can be used to optimize ventilator support beyond traditional monitoring. The determination of FRC and recruitability of the lung may assist the clinical team in identifying the best PEEP for each individual patient.

If the patient has a significant increase in PaO_2 associated with INO/placebo delivery, the clinical team can use that information to implement INO therapy as part of clinical care. It is unlikely that placebo will increase oxygenation appreciably. We will not unblind the study, the clinical team will have to make this decision based on a supposition of INO delivery.

Understanding the changes in respiratory function following TBI and the response to INO may improve treatment regimens for future patients.

10. Potential Risks, Discomforts, and inconveniences:

Level of risk: Greater than minimal risk.

The measurements to be made utilize non-invasive measures of lung volumes, flows, and pressures to determine mechanics.

Arterial puncture/venipuncture may cause pain/discomfort, bruising, fainting, and infection from phlebotomy sites.

Hypotension in severe pulmonary hypertension and left ventricular failure (very uncommon).

Methemoglobinemia has only been reported at 80ppm.

The stepwise increase in PEEP to determine changes in FRC will be limited to a maximum of 15 cm H_2O . PEEP can decrease venous return and cause transient hypotension. The risk of hemodynamic compromise at these low pressures is small. All subjects will have blood pressure and heart rate continuously monitored (as is standard of care) throughout the measurements.

Research personnel will remain at the bedside throughout the measurements of respiratory mechanics which will require approximately 30 minutes to complete.

11. Data Safety monitoring plan and/or DSMB:

[name] will act as medical monitor for the study. He will review subjects' research data and adverse events to ensure patient safety. The medical

monitor will have the power to temporarily or permanently halt enrollment if it is deemed that patient safety is compromised.

12. Data Analysis:

Descriptive statistics will be employed to summarize relevant patient demographic factors as well as on baseline measurement of clinical variables. As a check on the success of randomization, these variables will be compared between groups using t-tests or chi-square tests, as appropriate.

The primary endpoint for this study is a change in $\text{PaO}_2:\text{FiO}_2$ ratio of 20 percent or greater between baseline and Day 3. The proportions of patients achieving success according to this criterion will be compared between groups using a two-sided z-test with pooled variance.

Group sample sizes of 19 in group one and 19 in group two achieve 82% power to detect a difference between the group proportions of 0.40. The proportion in group one (the treatment group) is assumed to be 0.10 under the null hypothesis and 0.50 under the alternative hypothesis. The proportion in group two (the control group) is 0.10. The test statistic used is the two-sided Z test with pooled variance. The significance level of the test was targeted at 0.05. The significance level actually achieved by this design is 0.0361.

Respiratory mechanics will be presented as descriptive (Mean, SD, range). Up to 43 subjects may be enrolled, in order to obtain the required 38 evaluable subjects. Patients will be removed from the study and its analysis if extubated by the clinical treatment team during the 72 hour NO protocol.

13. Data storage and confidentiality (include sample storage if applicable)

We will ensure that paper forms are stored securely under lock and key when not in the direct custody of an investigator. Forms may have direct identifiers for the purposes of linking data from different medical records. Electronic data will not be entered with direct identifiers. A subject number will be used to link back to the identifier. The key linking identifier to subject number will not be stored with the electronic data. Electronic data will be stored in a password protected Redcap database. Analytical datasets will be stored on secure servers that also limit access to the investigator team. Should results of the study be published or reported, individual names or other identifying information will not be used. One year after the study and publication are complete the data will be destroyed.

14. Study Population

All subjects ≥ 18 and ≤ 75 years of age, admitted to the University of Cincinnati Medical Center with traumatic head injury requiring mechanical ventilation within 24 hours of admission will be screened for enrollment. Inclusion criteria will include:

1. TBI with head CT findings of injury by penetrating or blunt mechanism
2. Requiring mechanical ventilation within 24 hours of admission
3. Negative pregnancy test

Exclusion criteria will include:

1. Brain death
2. Expected survival < 48 hours
3. Pneumothorax causing chest tube to be placed
4. Elevated inspired oxygen concentration ($\text{FiO}_2 > 0.65$) on assessment
5. Hemodynamic instability (systolic BP < 100 mmHg, cardiac arrhythmias)
6. Uncontrolled ICP (>20 mmHg) necessitating bolus hypertonic saline therapy
7. Unilateral or bilateral pupil dilation and no reactive pupil
8. Spinal cord injury with hypotension
9. Severe ARDS ($\text{PaO}_2/\text{FIO}_2 < 100$)
10. Flail sternum or unilateral flail chest wall segment (2 places on ≥ 3 ribs)
11. Pulmonary contusion or lobar infiltrate visible on admission chest xray
12. Chronic lung disease with $\text{PCO}_2 > 60$ mmHg and $\text{HCO}_3^- > 32$ mmol/L
13. ICP >20 mmHg longer than 30 minutes despite hypertonic saline or mannitol therapy
14. Known heart failure (heart failure defined as EF < 20%)
15. CVP > 20 mm Hg with associated systolic blood pressure < 100 mmHg

15. Consenting process and plan

Study personnel will screen patients for inclusion and exclusion.

Due to the study population, all patients will be cognitively impaired due to their injuries, therefore surrogate consent will be obtained. Prior to approaching the patient's LAR/nok we will contact the patient's admitting physician and the ICU attending to assure their assent for patient enrollment.

The LAR/next of kin is identified using the social worker's note and contact information at the patient's bedside maintained by the nursing staff. Once the

LAR/next of kin is identified, the investigator and/or the study coordinator arranges to meet the LAR/next of kin in a private waiting room. The study staff allows the LAR/next of kin to decide if additional family members, friends, or advisors will be present. We frequently speak to the LAR/next of kin with a clergy member present or a family friend who has a medical background.

The informed consent, including the Health Insurance Portability and Accountability Act (HIPAA) authorization language approved by the University of Cincinnati and University of Cincinnati Medical Center's legal teams, is presented and reviewed to the LAR/nok and any questions are answered.

The study is time sensitive but LAR/nok will be allowed to review the consent document for 12 hours. A phone number is provided for the LAR/nok to call with additional questions. Subjects who cannot be enrolled during the first 36 hours after admission to UCMC will be considered screen failures.

Once subjects are deemed to be able to provide informed consent, the researchers will take them through the consenting process.

16. Compensation:

None.

17. Subject costs:

None.

18. Literature cited

2. Cooper KR, Boswell. PA. Reduced FRC and abnormal oxygenation in patients with severe head injury. *Chest* 1983;84:29-35.

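### Lung compliance is printed as pressure over volume, which is elastance, its reciprocal; nothing else in the plan gives the correct form or units

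*Combined protocol and SAP*

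**What the plan says.** Section 6 (Study design), item 1 names the measurement and gives its formula: "Static and dynamic lung compliance using tidal volume and airway pressures ($CL_{static} = P_{plat} - P_{PEEP}/VT". The dynamic version follows as "CL_{dynamic} = P_{plat} - P_{PEEP}/VT". In both, pressure comes first and tidal volume is the divisor.

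The next two items in the list are printed in the same style, without brackets. Airway resistance is "Raw = P_{plat} - P_{PEEP}/Mid Expiratory flow" and the dead space ratio is "V_d/V_t = PaCO_2 - PeCO_2/PaCO_2".

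On how values are obtained, section 6 says that the assessments are "accomplished using the existing monitors within the mechanical ventilator", and item 1 adds: "These measurements are made non-invasively using the integral monitoring of the mechanical ventilator". Section 10 describes the methods in general terms: "The measurements to be made utilize non-invasive measures of lung volumes, flows, and pressures to determine mechanics". Section 7 lists lung compliance among the recorded variables, without formula or units. It mentions both data sheets and the medical record as sources for what goes into the study database.

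Change in respiratory mechanics is a stated purpose (section 4). Items 5 to 7 of section 6 repeat the item 1 measurements at the PEEP steps, after gas delivery, and at day 3 in patients still ventilated. Section 12 plans to describe mechanics by mean, SD and range.

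**The concern.** Compliance is the volume gained per unit of pressure; elastance is the pressure needed per unit of volume. The plan names the one and writes the other. The Background (section 5) uses the term elastance only when reporting a cited study, and elastance is not listed as a study variable, so there is no sign that it was intended here.

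Anyone who follows item 1 exactly would enter elastance under the label of compliance. A lung that becomes easier to inflate would then show a falling value. The descriptive summaries would carry the wrong label, and changes across PEEP steps, after gas delivery and to day 3 would appear reversed. Section 9 says that the mechanics results are given to the clinical team, which is a further reason for label and quantity to agree.

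**Working it through.** **Inputs.** The formulas come from section 6, items 1 to 3. The plan states no compliance value, tidal volume or plateau pressure, so there is no figure of its own to reproduce. All pressures and volumes below are assumptions for illustration.

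**Step 1: can missing brackets explain it?** Read literally, item 1 subtracts a pressure-per-volume term from a pressure, which is dimensionally invalid. Items 2 and 3 have the same fault, so restore brackets around the numerator in all three:

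- Item 2: (Pplat − PEEP)/flow is pressure per flow, the right kind of quantity for a resistance.
- Item 3: (PaCO2 − PeCO2)/PaCO2 is a dimensionless ratio, the right kind of quantity for Vd/Vt.
- Item 1: (Pplat − PEEP)/VT is cmH2O per mL, which is elastance.

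The same repair works for items 2 and 3 and fails for item 1. Numerator and denominator are therefore exchanged there, in both the static and the dynamic formula.

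**Step 2: direction.** Assume VT 450 mL and PEEP 5 cmH2O, with plateau pressure falling from 20 to 17 cmH2O.

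- As printed, with brackets: (20 − 5)/450 = 0.0333 and (17 − 5)/450 = 0.0267 cmH2O/mL. Ratio 12/15 = 0.80, a fall of 20%.
- Compliance: 450/15 = 30 and 450/12 = 37.5 mL/cmH2O. Ratio 15/12 = 1.25, a rise of 25%.

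**Step 3: range.** Assume VT of 350 to 500 mL and Pplat − PEEP of 8 to 20 cmH2O.

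- Stiffest case: compliance 350/20 = 17.5 mL/cmH2O; printed form 20/0.350 = 57.1 cmH2O/L.
- Most compliant case: compliance 500/8 = 62.5 mL/cmH2O; printed form 8/0.500 = 16.0 cmH2O/L.

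The ordering reverses throughout, as it must for a reciprocal.

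**Step 4: can it be undone?** For each subject, 1/0.0333 = 30 and 1/0.0267 = 37.5, so static compliance is recovered exactly. The inversion has to come before averaging. Compliances of 30 and 60 have mean 45, but their reciprocals average (1/30 + 1/60)/2 = 0.025, and 1/0.025 = 40. The end points of a range invert exactly, in swapped order. For dynamic compliance, a reciprocal returns volume over whatever pressure difference was entered, so that pressure must also be known.

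**Step 5: is it corrected elsewhere?** Section 7 names the variable without formula or units. Sections 10 and 12 give neither. No section contains VT/(Pplat − PEEP).

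**The case against.** The strongest reply is that the formula may never be used. The wording of section 6 favours values read from the ventilator: item 3 says that dead space is to be calculated from an equation, while items 1, 2 and 4 describe measurements made by the ventilator's own monitoring. Section 7 can also be read as taking compliance from the medical record. On that reading the slip does not touch the data. This argument largely stands as to consequence, but it is not conclusive. Item 1 itself says that tidal volume and airway pressures are used and supplies formulas, study staff make the measurements, and section 7 also sends mechanics to data sheets.

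A second reply is that the harm would be reversible in any case. That stands: mechanics data are entered per subject in the study database, so the investigators could take reciprocals before summarising. Only someone holding nothing but a published mean and SD would be stuck. Any percentage put on that reader's error would rest on assumed distributions and on a conversion that the plan does not propose.

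A third reply concerns PDF reading. A reader might infer from the identical static and dynamic formulas that the trial does not distinguish the two. The available text cannot support that. The repeated plateau term may be a reading fault; item 3 likewise shows "alveolar concentrations ($PaCO_2" with the symbol it uses for arterial CO2. This limits what can be said about the dynamic pressure term. It does not explain pressure standing over volume in both formulas.

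**Conclusion.** The printed definition of lung compliance is inverted, and nothing in the plan corrects it. Confidence in that is high, because it depends only on the order of terms, which is the same in both formulas.

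The effect on data is conditional. If values are calculated from item 1, the mean, SD and range reported as compliance describe elastance, and changes run the wrong way (−20% against +25% in the assumed example). If displayed compliance is recorded, the data are unaffected. A reader might infer that the compliance results will be wrong or cannot be recovered; the documents support neither, since they leave the source of the value open and provide for subject-level data.

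The primary endpoint is based on PaO2:FiO2, and compliance does not enter it, its test or the sample size. Compliance is one of several descriptive mechanics variables. The point is minor: a wrong operational definition that is easy to correct.

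**What to change.** 1. In section 6, item 1, write static compliance as VT/(Pplat − PEEP), in mL/cmH2O, with brackets.
2. Write dynamic compliance as volume over pressure. After checking the original PDF, define the pressure term that distinguishes it from static compliance.
3. State whether the recorded value is the ventilator's displayed compliance or is calculated from the formula.
4. If any values have already been calculated from the printed formula, convert them subject by subject before summarising.

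Brackets in items 2 and 3 could be added at the same time as an editorial matter. The cost is two corrected formulas and one added sentence, with no change to the primary endpoint, sample size or visits.

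### Static and dynamic compliance are given the same plateau-pressure expression, and the ratio is inverted, so dynamic compliance is not measured as defined

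*Combined protocol and SAP*

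**What the plan says.** Section 6, item 1 of the combined protocol and SAP introduces two variables: "Static and dynamic lung compliance using tidal volume and airway pressures". It defines the first as "CL_{static} = P_{plat} - P_{PEEP}/VT" and the second as "CL_{dynamic} = P_{plat} - P_{PEEP}/VT". Item 2 gives airway resistance as "Raw = P_{plat} - P_{PEEP}/Mid Expiratory flow". For both items the source is stated as follows: "These measurements are made non-invasively using the integral monitoring of the mechanical ventilator".

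These variables recur through the study. Item 5 has them measured during the PEEP titration. Item 6 states: "After receiving the placebo or inhaled NO, the measurements in #1-4 will be reassessed". Item 7 repeats the sequence on day 3 for patients still ventilated.

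They serve the first aim in section 4 (Purpose of Study): "To determine the changes in respiratory mechanics in patients with traumatic brain injury". Section 12 (Data Analysis) limits the analysis to summary statistics: "Respiratory mechanics will be presented as descriptive (Mean, SD, range", with no between-group test. Section 7, which lists the data to be recorded, mentions lung compliance without separating static from dynamic.

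**The concern.** Two variables listed separately should be able to differ. Dynamic compliance is conventionally taken at peak inspiratory pressure and static compliance at plateau pressure, so the distance between them reflects the inspiratory resistive load. With plateau pressure in both definitions, that information is gone.

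The orientation of the ratio is a second fault in the same line. A compliance is volume per unit pressure; the printed expressions put pressure on top. A quantity of that form rises as the lung stiffens, whereas a compliance falls. The background in section 5 reports elastance from a cited study of brain-injured patients. A reader who compares this trial's table with such work could therefore mistake both the quantity and its direction.

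At stake is one of the variables under a stated aim, at every occasion on which items 1-4 are measured. The inversion can be undone patient by patient if plateau pressure, PEEP and tidal volume are kept, though not from a published mean and SD, because the mean of reciprocals is not the reciprocal of the mean. A peak pressure that nobody recorded may not be recoverable at all.

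**Working it through.** The plan reports no compliance figure to reproduce, so the check is a comparison of definitions followed by an illustration.

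**1. Term-by-term comparison (section 6, item 1)**

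| Variable | Pressure term | Subtracted term | Divisor |
|---|---|---|---|
| Static | Pplat | PEEP | VT |
| Dynamic | Pplat | PEEP | VT |

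All three terms match. For any Pplat, PEEP and VT, static minus dynamic = 0. This needs no outside convention. Turning both ratios the right way up would leave them identical.

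**2. Search for another definition.** No other section defines dynamic compliance, and peak inspiratory pressure is named nowhere. The resistance formula in item 2 also uses Pplat and PEEP, over mid-expiratory flow, so none of the formulas in items 1-4 contains the peak-to-plateau component.

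**3. Orientation and brackets.** Assumed inputs, not in the documents: VT 420 mL, Pplat 20 cm H2O, PEEP 5 cm H2O.

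- As printed, with division first: 20 - 5/420 = 19.99, which mixes units and has no physical meaning.
- With the evident brackets: (20 - 5)/420 = 0.036 cm H2O/mL, an elastance.
- As a compliance: 420/(20 - 5) = 28.0 mL/cm H2O, the reciprocal of the line above.

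**4. Illustrative size.** Same assumed inputs. Dynamic compliance = VT/(Ppeak - PEEP), with Ppeak = Pplat + gap; static compliance = 28.0.

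| Assumed gap (cm H2O) | Dynamic (mL/cm H2O) | Below static |
|---|---|---|
| 0 | 420/15 = 28.0 | 0% |
| 2 | 420/17 = 24.7 | 12% |
| 5 | 420/20 = 21.0 | 25% |
| 10 | 420/25 = 16.8 | 40% |
| 15 | 420/30 = 14.0 | 50% |

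The two coincide only when the gap is zero.

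**5. Reach.** The primary endpoint in section 12 is a change in the PaO2:FiO2 ratio, compared by a two-sided pooled z-test. Exact binomial enumeration with 19 per group and proportions of 0.50 and 0.10 gives power 0.815 (stated 82%). With 0.10 in both groups it gives a significance level of 0.0361 (stated 0.0361). Both reproduce, and compliance enters neither.

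**The case against.** The best defence is that this is a slip of notation with little practical effect. Naming two variables shows that two were intended. The values come from the ventilator's own monitoring, and section 6 also places a respiratory monitor for continuous recording. The devices may therefore supply a proper dynamic value, and staff may never use the printed expression.

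Part of this stands. A reader might infer that dynamic compliance is never measured in this trial. The documents do not support that: they do not say that compliance is calculated by hand, nor what the devices display. The supportable statement is that it is not measured as defined. The device argument does not remove the fault, since the printed expression is the only definition given and no section refers to a device-reported alternative.

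A misread subscript in the text taken from the PDF cannot be excluded. Item 1 has an unmatched bracket, and item 3 uses one symbol for both arterial and alveolar CO2. But Pplat appears in the same way in all three pressure formulas, and nothing positively points to a misread. If the source file does show a peak-pressure term for dynamic compliance, the duplication falls away and the orientation and brackets remain to be corrected.

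A reader might also infer that airway resistance goes unassessed. It does not: item 2 makes it a separate variable. What is missing is narrower, namely any formula that uses peak pressure.

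Finally, a reader might take the percentages above as this trial's error. They cannot be, because every pressure and volume behind them is assumed.

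**Conclusion.** The point holds in limited form. Item 1 gives two named variables one expression, so their difference is zero by construction, and that expression is the reciprocal of a compliance, printed without brackets. The zero difference follows from the text alone.

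The 12% to 50% range depends on the assumed tidal volume and pressures and on the usual peak-pressure definition of dynamic compliance. It shows that the omission need not be negligible and says nothing about its actual size in these patients.

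The consequence stays within the descriptive mechanics objective. The documents give no ground for extending it to the oxygenation endpoint, the power statement or the randomised comparison on that endpoint. It is worth correcting because the definition is operative and is reused throughout the measurement sequence, but it does not threaten the trial's main result.

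**What to change.** In section 6, item 1, replace both expressions, with brackets:

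- static compliance = VT/(Pplat - PEEP)
- dynamic compliance = VT/(Ppeak - PEEP)

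Both must change together. Correcting only the dynamic line would set a volume-over-pressure value beside a pressure-over-volume one. Add peak inspiratory pressure to the data sheet and database at every occasion on which items 1-4 are measured, and have section 7 list static and dynamic compliance separately. If device-reported values are to be used instead, name the device and state its definition.

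In the same edit, check the resistance formula in item 2, which uses the same Pplat and PEEP terms and also lacks brackets, and confirm which pressure difference belongs with mid-expiratory flow.

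The cost is one corrected line of definitions, one added data field and a check of item 2. The documents do not say whether the ventilator displays peak pressure, so confirm that first. Where patients have already been studied, check whether stored recordings hold it. No change to the sample size, the primary analysis or the study procedures follows.
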